57 insulin degludec for the treatment of patients with diabetes. Insulin degludec, a long-acting basal
58 insulin analog with a half-life of >25 hours and activity of >40 hours^{18,19}, results in comparable
59 glycemic control to glargine¹⁹⁻²¹, but with lower rates of hypoglycemia^{19,20,22}. The efficacy and
60 safety of degludec is well documented in ambulatory patients; however, no studies have assessed
61 the safety and efficacy of these new formulations in the hospital setting. Although we can
62 anticipate a reduced number of hypoglycemic events with insulin degludec, certain features
63 needs to be investigated in the hospital including 1) prolonged duration of action, which may
64 limit the ability to make day-to-day adjustments in insulin dosage; 2) a steady-state insulin
65 concentration achieved after second or third day of therapy^{21,23}; and limited safety data in
66 acutely ill patients with altered nutritional status. Accordingly, the present pilot randomized trial
67 will compare the efficacy and safety of a basal bolus regimen with degludec U100 and glargine
68 U100 in medicine and surgery patients with type 2 diabetes (T2D).

69
70 **Significance and Innovation.** Degludec is a new generation basal insulin analog with a longer
71 duration of action compared to insulin glargine^{18,19}. Several outpatient trials have reported that
72 treatment with degludec results in comparable improvement in HbA1c levels and in lower rates
73 of hypoglycemia compared to glargine U100 insulin. No previous studies; however, have
74 compared the safety and efficacy of the long-acting basal insulin degludec in the inpatient
75 management of patients with diabetes. It is expected that a large number of patients with diabetes
76 will be started or transitioned to this new insulin formulation; so acquiring knowledge on their
77 safety and efficacy is of great clinical interest. Accordingly, the proposed study will provide
78 novel and clinically useful information on the efficacy (BG control) and safety (hypoglycemia)
79 of degludec in the inpatient setting and after hospital discharge in general medicine and surgery
80 patients with T2D.

81

82 **II. SPECIFIC OBJECTIVES:**

83 **Objective 1. To determine differences in inpatient glycemic control, as measured by mean**
84 **daily blood glucose concentration and the frequency of hypoglycemia in general medicine**
85 **and surgery patients with T2D treated with basal bolus regimen with insulin degludec or**

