86 **glargine once daily plus aspart insulin before meals.** We will analyze a total of 180 subjects
87 with T2D treated prior to admission with diet, oral hypoglycemic agents, short-acting GLP1-RA
88 (except long-acting exenatide, dulaglutide and albiglutide), or insulin therapy (except degludec
89 and glargine U300) will be included in this prospective, randomized, open label trial to compare
90 the safety and efficacy of a basal bolus regimen with degludec and glargine in patients with T2D
91 admitted to general medicine and surgery services. Secondary end points include length of stay,
92 hospital complications, and hospital readmissions.

93
94 **Objective 2: To determine differences in glycemic control after hospital discharge between**
95 **treatment with degludec and glargine in medicine and surgery patients T2D.** Patients with
96 poorly controlled diabetes (HbA1c $\geq 7.0\%$) enrolled in Aim 1 will be invited to participate in this
97 open label prospective outpatient study. At hospital discharge, patients will be treated following
98 an HbA1c based algorithm²⁴ for a total duration of the outpatient follow-up of 3 months (see
99 hospital discharge algorithm, page 7).

100

101 **III. RESEARCH DESIGN AND METHODS**

102 **III.A Study Hypothesis (hypotheses):**

103 **Hypothesis #1:** Treatment with degludec and glargine will result in equivalent glycemic control
104 in general medicine and surgery patients with T2D. Degludec will result in lower number of
105 hypoglycemia compared to glargine.

106
107 **Hypothesis:** treatment with degludec and glargine will result in a similar improvement in HbA1c
108 levels after hospital discharge. Degludec will result in lower number of hypoglycemia compared
109 to glargine.

110

111 **III.B Endpoints:**

112 **The primary endpoint** of the trial is non-inferiority in mean differences between treatment groups
113 in their mean blood glucose concentrations during the first 10 days of therapy (non-inferiority
114 will be determined at a difference < 18 mg/dl). All participants who receive ≥ 2 doses of study
115 drug will be included in the analysis.

116

117 **Secondary outcomes** include differences between treatment groups in any of the following
118 measures: Endpoints 1-4 (glycemic control) will be analyzed during the first 10 days of therapy
119 and endpoints 5, 7, 8, and 9 (length of stay and complications) will be analyzed during hospital

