120 stay. Endpoint 6 (readmissions) will be evaluated up to 12 weeks after hospital discharge.

121 1. Proportion of BG readings between 70 mg/dl and 180 mg/dl before meals

122 2. Number of hypoglycemia (< 70 mg/dl and 54 mg/dl) and severe hypoglycemia (< 40 mg/dl)
123 episodes during the first 10 days of therapy in the inpatient setting.

- 124 3. Number of episodes of severe hyperglycemia (BG > 240 mg/dl) after the first day of treatment
125 until the tenth day of therapy
- 126 4. Daily dose of basal insulin, daily dose of prandial insulin, and total daily dose
- 127 5. Length of hospital stay.
- 128 6. Number of readmissions (hospitalization) and Emergency room visits.
- 129 7. Cardiac complications are defined as myocardial infarction, cardiac arrhythmia requiring
130 medical treatment, or cardiac arrest.
- 131 8. Acute kidney injury defined as an increment in serum creatinine ≥ 0.3 mg/dL from baseline or
132 ≥ 1.5 times baseline creatinine (KDIGO) ²⁵.
- 133 9. Hospital mortality.

134

135 III.C Study type:

136 This is a prospective, randomized, open label multicenter trial to compare the safety and efficacy
137 of a basal bolus regimen with degludec and glargine in patients with T2D admitted to general
138 medicine and surgery services.

139

140 This study will include male or female subjects > 18 years. Due to the design of this hospital
141 study, there will be no run-in period. Upon arrival to the emergency department or medical or
142 general surgical wards, subjects will be screened. A total of 180 subjects will be analyzed. A
143 maximum of 108 (60%) surgical or medical patients will be randomized in the study to ensure a
144 balanced proportion of each group is included. Patients with a known history of T2D treated with
145 diet alone, any combination of OADs, short acting GLP-1 RA (liraglutide or exenatide) and
146 insulin prior to admission will be considered potential candidates for this study. Patients treated
147 with degludec, glargine U300 or with long-acting GLP1-RA (dulaglutide, albiglutide and weekly
148 exenatide) prior to admission will be excluded. Patients admitted with acute or chronic medical
149 illnesses, emergency or elective surgical procedures and trauma would be included in the study.

150

151 Insulin therapy will be aimed to maintain fasting and pre-meal blood glucose levels between 100
152 mg/dl and 180 mg/dL while avoiding hypoglycemia. Blood glucose levels between 70 and 100

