182 BG concentration during insulin treatment is 100-180 mg/dl. The daily basal (degludec/glargine)
183 dose will be increased by 10% if the fasting BG is between 180 and 240 mg/dl or by 20% if
184 fasting BG concentration is >240 mg/dL. The total daily insulin dose (basal and prandial insulin)
185 will be increased by 20% in patients with mean BG > 240 mg/dl. In addition, the basal insulin
186 dose will be reduced by 10% if any BG is between 70-100 mg/dl, and by 20% in patients with
187 any BG < 70 mg/dl. The total daily dose will be reduced 30-40% in the event of severe
188 hypoglycemia (BG < 40 mg/dl).

189 Several clamp studies in patients with type 1 and type 2 diabetes and observations from clinical
190 practice showed that insulin degludec quickly reaches steady state after the 2nd or 3rd day of
191 therapy, a similar period reported with other basal insulin analogs^{26,27}. Based on its steady-state
192 condition, clinical pharmacology studies show that insulin degludec has a flatter, less variable
193 and more consistent glycemic effect.

194 **Treatment randomization.** Patients will be randomized using a computer-generated
195 randomization table. Treatment randomization/assignment will be coordinated by the research
196 pharmacy. A research pharmacist at each institution will follow a computer-generated block
197 randomization table based on glucose levels (BG≤200 or BG>200) at randomization.
198

199 **TREATMENT PROTOCOL - Basal Bolus Insulin Regimen with Degludec or Glargine** 200 **Once Daily plus Aspart before Meals**

201 **Patients Treated with Insulin Prior to Admission**

- 203 • Discontinue oral antidiabetic drugs on admission.

204 Subjects treated with insulin prior to admission will receive 80% or 100 % of the total daily
205 dose (TDD) given as basal bolus regimen.

206

207 **Starting Insulin Doses:**

- 208 - **BG < 200 mg/dl give 80% of TDD***
- 209 - **BG ≥ 200 mg/dl give 100% of TDD***

210

- 211
212 • Half of TDD will be given as degludec or glargine and half as rapid-acting insulin.
213 • Degludec and glargine will be given once daily at the same time of the day
214 • Patients will receive the full-dose of degludec or glargine (even if NPO) the day of
215 surgery or diagnostic procedure(s).
216 • Aspart insulin will be given in three equally divided doses before each meal. To prevent
217 hypoglycemia, if a subject is not able to eat, aspart insulin dose will be held.

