361 admitted to the hospital with an acute medical/surgical illness.

362 **Planned number of subjects to be randomized/started on study medication(s):** 180

363 **Anticipated number of trial sites:** 3 sites (Emory University Hospitals/Grady Hospital in
364 Atlanta, GA; additional Sites: Mount Sinai, NY-PI: [name] and Providence Medical
365 Research Centre PI: [name])

366 **Anticipated number of subjects to be randomised/started on trial medication(s) at each**
367 **trial site:** 60.

368 **Country planned to participate:** United States.

369

370 **Inclusion Criteria**

- 371 1. Males or females between > 18 years admitted to a general medicine or surgical service.
- 372 2. A known history of T2D treated either with oral monotherapy, any combination of oral
373 antidiabetic agents, short-acting GLP1-RA (exenatide, liraglutide) or insulin therapy
374 except for degludec and glargine U300.
- 375 3. Subjects with diet alone and HbA1c>7.0%
- 376 4. Medical and surgical patients expected to be admitted (LOS) longer than 2 days
- 377 5. Subjects must have a randomization BG > 140 mg and < 400 mg/dL without laboratory
378 evidence of diabetic ketoacidosis (bicarbonate < 18 mEq/L, pH < 7.30, or positive serum
379 or urinary ketones).
- 380 6. Signed, informed consent and HIPAA documentation prior to any study procedures

381

382 **Exclusion Criteria**

- 383 1. Subjects with increased BG concentration, but without a known history of diabetes (stress
384 hyperglycemia).
- 385 2. Subjects treated with diet alone (no antidiabetic agents) and admission HbA1c <7%.
- 386 3. Admission or pre-randomization BG≥400 mg/dl
- 387 4. Subjects with a history of diabetic ketoacidosis and hyperosmolar hyperglycemic state, or
388 ketonuria ³².
- 389 5. Patients treated with degludec or glargine U300, or with long-acting weekly GLP1-RA
390 (weekly exenatide, dulaglutide or albiglutide).
- 391 6. Patients with acute critical or surgical illness admitted to the ICU, except for observation
392 (<24 hours and did not require vasopressors and/or mechanical ventilation).
- 393 7. Patients with history of clinically relevant hepatic disease (diagnosed liver cirrhosis and
394 portal hypertension), ongoing corticosteroid therapy (equal to a prednisone dose ≥5
395 mg/day), or impaired renal function (eGFR< 30 ml/min), or congestive heart failure
396 (NYHA- IV).
- 397 8. Mental condition rendering the subject unable to understand the nature, scope, and

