488 juice/snack (crackers) as per protocol. If the patient is not awake: 50ml (1 amp) will be given
489 STAT. Blood glucose levels will be repeated in 15 minutes and dextrose administration will be
490 repeated as needed for values < 70 mg/dl.

491

492 **Subject Compliance**

493 Aim 1. Inpatient (hospital) trial. We will use electronic medical records and nursing records to
494 document day and time of insulin administration of study drug (degludec and glargine) given
495 once daily and prandial- rapid-acting insulin (aspart) given before meals. We will also record
496 dose and number of units given as supplement (correction) to correct hyperglycemia.

497

498 Aim 2. Patients will be contacted every 2 weeks after discharge by a study coordinator to assess
499 insulin administration, glycemic control, hypoglycemia and medication adherence. Patients are
500 to bring all used and unused insulin pens (study drug). Patients will keep daily record of time
501 and dose of insulin administered every day during the study period.

502

503 **VI. STATISTICAL CONSIDERATIONS:**

504 **VI.A Aim 1. To determine differences in inpatient glycemic control in patients treated with**
505 **degludec or glargine in patients with T2D.**

506 **Sample Size and Power Calculations:**

507 The primary endpoint in this study is glycemic control measured by mean daily BG
508 concentration. To show the non-inferiority of degludec and glargine in terms of glycemic
509 control, we set the equivalence margin as 18 mg/dl (1 mosm/l), from a view that a difference <18
510 mg/dl is usually not considered as clinically significant^{12-14,37}. Based on the results of the Rabbit
511 medicine and surgery trials, it is reasonable to assume the standard deviation of mean daily BG is
512 bounded above by 45 mg/dl. Assuming the true BG difference between the treatment groups is
513 zero, and using one-sided, two-sample t-tests, we require 78 subjects for each treatment group to
514 achieve 80% power with alpha=0.05. Accounting for 10-14% attrition rate, we would need 90
515 patients per treatment group, which means 180 subjects in total, to achieve >80% power in Aim
516 1.
517

518 **Analysis of Primary Endpoint:**

519 The primary endpoint for Aim 1 is non-inferiority in mean differences between treatment groups
520 in their mean blood glucose concentrations during the first 10 days of therapy (non-inferiority

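### The primary non-inferiority mean starts on day 1 of therapy, so a difference between arms that emerges later may be diluted in short stays; a day-2-to-10 analysis should be prespecified

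*Combined protocol and SAP*

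**What the plan says.** III.B Endpoints defines the primary comparison as the difference between arms "in their mean blood glucose concentrations during the first 10 days of therapy (non-inferiority" margin 18 mg/dl). VI.A, Analysis of Primary Endpoint, repeats this window. Neither place excludes day 1 or limits day-1 readings to those after the first study basal dose.

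Other parts of the plan bear on day 1:

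- **Flow chart, Aim 1.** Consent, randomisation and pre-meal glucose are all marked on hospital day 1. Fasting glucose and dose adjustment start on day 2.
- **Inclusion criterion 5.** Randomisation glucose must be above 140 and below 400 mg/dl.
- **Steady state.** The background describes a steady-state insulin "concentration achieved after second or third day of therapy". The titration text in III.C says that clinical "practice showed that insulin degludec quickly reaches steady state after the 2nd or 3rd day of" therapy, and that other basal analogs take a similar time.
- **Length of exposure.** Inclusion criterion 4 reads "Medical and surgical patients expected to be admitted (LOS) longer than 2 days". The analysis set in III.B is "All participants who receive ≥ 2 doses of study" drug.
- **Secondary endpoint 3.** It reads "Number of episodes of severe hyperglycemia (BG > 240 mg/dl) after the first day of treatment", so this glycaemic endpoint leaves day 1 out.

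**The concern.** In a non-inferiority comparison, anything that makes the arms look alike helps the claim. Early readings come close to entry glucose, before any dose adjustment and before steady state. Both arms also share the same starting-dose rules, prandial insulin and correction scale. If the arms are more alike on day 1 than later, including day 1 pulls a later difference toward zero. The pull is strongest in short stays: day 1 is one third of a 3-day stay and one tenth of a 10-day stay. At stake is whether a result inside 18 mg/dl can be read as evidence about control once treatment is established. The plan already leaves day 1 out of endpoint 3 and gives no reason for treating the primary endpoint differently.

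**Working it through.** **Inputs from VI.A.** The margin is 18 mg/dl ("control, we set the equivalence margin as 18 mg/dl (1 mosm/l), from a view that a difference <18" mg/dl is not clinically significant). The SD is 45 mg/dl ("bounded above by 45 mg/dl. Assuming the true BG difference between the treatment groups is" zero). The test is a one-sided two-sample t-test at alpha 0.05 with 80% power, 78 per arm, and 90 per arm after attrition.

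**The plan's own figure.** n per arm = 2 × 45² × (1.645 + 0.842)² / 18² = 12.5 × 6.18 ≈ 77.3, rounded up to 78. The exact noncentral t gives 80.0% power at 78 per arm and 84.8% at 90. The stated sample size is correct. The issue is the window.

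**Dilution formula.** Let D be the difference (degludec minus glargine) from day 2 onward, f × D the difference on day 1, and k the stay in days. With days weighted equally, the expected difference in the k-day mean is D × (k − 1 + f) / k.

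**Chance of declaring non-inferiority.** P = Φ((18 − diluted difference)/SE − 1.645), with SE = 45 × √(2/78) = 7.2 mg/dl.

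**Worked case.** For k = 3, f = 0 and D = 18, the diluted difference is 18 × 2/3 = 12.0. Then P = Φ(6.0/7.2 − 1.645) = 20.8%.

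**Results with D = 18 mg/dl (at the margin), 78 per arm, every patient staying k days.** Cells show the averaged difference in mg/dl and P.

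| Day-1 difference (assumed) | 3 days | 5 days | 10 days |
|---|---|---|---|
| None (f = 0) | 12.0; 20.8% | 14.4; 12.6% | 16.2; 8.1% |
| Half of later (f = 0.5) | 15.0; 11.0% | 16.2; 8.1% | 17.1; 6.4% |
| Equal to later (f = 1) | 18.0; 5.0% | 18.0; 5.0% | 18.0; 5.0% |
| 1.5 times later (f = 1.5) | 21.0; 2.0% | 19.8; 2.9% | 18.9; 3.8% |

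**Other cases.**

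- With 90 per arm and f = 0, P is 22.6%, 13.4% and 8.4% for 3, 5 and 10 days.
- A 2-day stay, the floor implied by the two-dose rule with once-daily basal insulin, gives 9.0 mg/dl and 34.6% at 78 per arm with f = 0.
- The plan does not say whether days or readings are weighted. Assume that readings are pooled, with two on day 1, four on each later day, and f = 0. A 3-day stay then gives 18 × 8/10 = 14.4 mg/dl and 12.6%. A 10-day stay gives 18 × 36/38 = 17.1 mg/dl and about 6.5%.

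**With day 1 left out.** A constant 18 mg/dl from day 2 stays at 18 mg/dl, and P is the nominal 5% for any stay, provided that SD 45 still applies.

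**The case against.** Four arguments on the other side have weight.

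1. **No passage says that day-1 readings cannot differ.** A reader might infer from the steady-state statements that the study basal insulin cannot separate the arms on day 1. Being below steady state is not the same as having no effect. Only readings before the first basal dose are certain to carry no treatment effect. This stands.

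2. **The direction could reverse.** The background gives degludec a half-life above 25 hours and lists the time to steady state among the features to be investigated in hospital. If slow build-up made early control worse on degludec, day 1 would carry the larger difference, and leaving it out would favour non-inferiority. This stands, and the last row of the table shows it.

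3. **The plan's target is the average over the first 10 days of therapy.** A reader might take 21% as the type I error of the planned test. It is not. If the true averaged difference is 12 mg/dl, calling it less than 18 is correct for that average. The percentages are errors only against a day-2-onward target.

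4. **The plan has partial safeguards.** VI.A includes by-day comparisons and repeated-measures models, which could reveal a later difference, and randomisation is stratified by glucose at 200 mg/dl. None of these is a day-2-onward non-inferiority test.

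Endpoint 3 is also an imperfect precedent. Its threshold of 240 mg/dl lies inside the permitted entry range, so counting day 1 there would pick up presenting hyperglycaemia, and the other glycaemic endpoints use the first 10 days.

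**Conclusion.** The point holds as a weakness in the choice of window. It does not show an error in the sample size or a miscalibrated test for the 10-day average. The primary mean mixes start-up with established treatment, and the plan prespecifies no non-inferiority result for the later period alone.

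If the day-1 difference is zero, a later difference at the margin passes with probability 21% (3-day stays) down to 8% (10-day stays). If half is already present, the range is 11% to 6%. If day 1 carries 1.5 times the later difference, it is 2% to 4%. These figures assume a constant difference from day 2, equal stays, SD 45 mg/dl for every window and 78 per arm. The documents give no length-of-stay distribution, so the size can only be stated as a range. The unknown direction is itself a reason to prespecify how day 1 is handled.

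**What to change.** In III.B and VI.A:

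1. Prespecify a non-inferiority analysis of mean glucose from day 2 to day 10 with the same 18 mg/dl margin. Preferably make it primary, in line with endpoint 3, and report the day 1 to 10 mean as supportive. At the least, make it a key sensitivity analysis that must agree before non-inferiority is claimed.
2. In every version, exclude readings taken before the first study basal dose.
3. Adjust the comparison for pre-dose randomisation glucose, which is already collected and is the stratification variable. Do not adjust for day-1 readings after the dose, because they can carry treatment effect.

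**Cost.** This needs wording and analysis work but no new data. First-day control carries less weight, and patients with short stays contribute fewer readings. The SD bound of 45 mg/dl should be rechecked for the shorter window. If it holds, 78 per arm (90 with attrition) still serves the day-2-to-10 analysis as primary.
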